17.4. VITAL SIGNS

The following vital signs measurements will be reported for this study:

- Supine Systolic Blood Pressure (mmHg)
- Standing Systolic Blood Pressure (mmHg)
- Supine Diastolic Blood Pressure (mmHg)
- Standing Diastolic Blood Pressure (mmHg)
- Supine Pulse Rate (beats/min)
- Standing Pulse Rate (beats/min)
- Respiratory Rate (breaths/min)
- Temperature (°C)
- Weight (kg)
- BMI (kg/m²)
- Waist Circumference (cm)

The following summaries will be provided for vital signs data:

- Observed value and change from baseline by visit
- Observed value and change from baseline by visit by BMI category at both DB baseline and OL baseline:
 - o Underweight: <18.5
 - o Normal: 18.5 to <25.0
 - o Overweight: 25.0 to <30.0
 - o Obese: >=30.0
- Number and percentage of subjects with at least one post-OL baseline PCS value for selected vital signs parameters (Table 4). The period of evaluation includes both OL treatment period and OL follow-up period.

Both the DB baseline and the OL baseline will be used in the calculation of change values.

All vital signs data will be provided in data listings.

Document: Documentation\SAP

Author:

Version Number:
 Version Date:

Final V1.0
 27FEB2019

Template No: CS_TP_BS016 Revision 4
 Effective Date: 01Apr2016

Reference: CS_WI_BS005

Table 4. PCS Criteria for Vital Signs Parameters

Parameter Name	PCS Low	PCS High
Systolic Blood Pressure (mmHg)	Value ≤ 90 and ≥ 20 decrease from baseline	Value ≥ 180 and ≥ 20 increase from baseline
Diastolic Blood Pressure (mmHg)	Value ≤ 50 and ≥ 15 decrease from baseline	Value ≥ 105 and ≥ 15 increase from baseline
Pulse Rate (beats/min)	Value ≤ 50 and ≥ 15 decrease from baseline	Value ≥ 120 and ≥ 15 increase from baseline
Weight (kg)	$\geq 7\%$ decrease from baseline	$\geq 7\%$ increase from baseline
Temperature ($^{\circ}\text{C}$)	NA	Value $\geq 38.3^{\circ}\text{C}$ and $\geq 0.8^{\circ}\text{C}$ increase from baseline

17.4.1. ORTHOSTATIC EFFECTS

Orthostatic hypotension is defined as a decrease of ≥ 20 mmHg in systolic blood pressure or ≥ 10 mmHg in diastolic blood pressure after the subject had been standing for at least 2 to 4 minutes, compared to the systolic blood pressure and diastolic pressure measured in the supine position, respectively.

Orthostatic tachycardia is defined as a heart rate increase of ≥ 20 beats per minute (bpm) and a heart rate of >100 bpm after the subject was standing for at least 2 to 4 minutes, compared to the heart rate measured in the supine position.

The number and percentage of subjects with orthostatic hypotension and orthostatic tachycardia will be summarized for DB baseline, OL Baseline, and the overall post OL baseline period, as well as by visit. As specified in section 6.4 of the statistical analysis plan, any orthostatic hypotension or tachycardia events that occurred at the early termination visit will be assigned to the next planned visit.

17.5. OTHER SAFETY ASSESSMENTS

17.5.1. MOVEMENT DISORDER MEASURES

Abnormal Involuntary Movement Scale (AIMS)

The AIMS is a clinician-rated assessment of abnormal movements. It contains 12 items that assess facial and oral movements (items 1 - 4), extremity movements (items 5 - 6), trunk movements (item 7), global judgments (items 8 - 10) and dental status (items 11 - 12). AIMS total score will be calculated as the sum of items 1 through 7 (ranging from 0 to 28). Higher values of AIMS total score indicate increased severity in abnormal movement. If any item score contributing to the calculation of AIMS total score is missing, the total

Document: Documentation\SAP

Author:

Version Number:

Final V1.0

Version Date:

27FEB2019

Template No: CS_TP_BS016 Revision 4
 Effective Date: 01Apr2016

Reference: CS_WI_BS005

Copyright © 2009, 2010, 2012, 2016 Quintiles Transnational Corp. All rights reserved.

The contents of this document are confidential and proprietary to Quintiles Transnational Corp. Unauthorized use, disclosure or reproduction is strictly prohibited.

Statistical Analysis Plan

score will be set to missing. Items 8 through 12 will not be used in total score calculation. The global severity score (item 8) will be summarized separately.

The observed values of AIMS total score at both the DB baseline and the OL baseline, and at each scheduled post-OL baseline extension visit and LOCF, will be summarized for the safety population. Changes from baseline in these measures will also be summarized for each scheduled post-OL baseline extension visit and LOCF, using both the DB baseline and the OL baseline to calculate the change values.

In addition, the AIMS total score at each visit will be classified as “abnormal” if: either at least two items (out of items 1 - 7) have a response of “mild” or higher, or at least one item (out of items 1 - 7) has a response of “moderate” or higher. Otherwise, the non-missing total score will be classified as “normal”. This is a modification of the Schooler-Kane criteria for tardive dyskinesia. Shifts from baseline in AIMS total score classification will be summarized by visit and overall for all post-OL baseline assessments during the open-label extension period, using both the DB baseline and the OL baseline.

The AIMS global severity score (item 8) will be summarized both numerically and categorically by visit.

The post-OL baseline AIMS global severity assessment will be classified as “worsened” (score is higher than baseline), “unchanged” (score is equal to baseline), or “improved” (score is lower than baseline), relative to a subject’s baseline response. These post-OL baseline changes will be summarized by visit, using both the DB baseline and the OL baseline.

Barnes Akathisia Rating Scale (BARS)

The BARS is a clinician-rated assessment to measure the observable, restless movements that characterize drug-induced akathisia. It contains 4 items: an objective rating (objective restlessness), 2 subjective ratings (awareness of restlessness, distress related to restlessness), and a global clinical assessment of akathisia. The subjective and objective items (items 1 through 3) will be summed to yield the BARS total score (ranging from 0 to 9). Higher values of BARS total score indicate higher severity of akathisia. If any item score contributing to the calculation of BARS total score is missing, the total score will be set to missing. The global clinical assessment rating will be analyzed separately.

BARS total score (observed value and change from both the DB baseline and the OL baseline) will be summarized numerically by visit. In addition, the BARS item scores for the four items will be summarized both numerically and categorically by visit.

The post-OL baseline BARS global clinical assessment of akathisia will be classified as “worsened” (score is higher than baseline), “unchanged” (score is equal to baseline), or “improved” (score is lower than baseline), relative to a subject’s baseline response. These post-OL baseline changes will be summarized by visit, using both the DB baseline and the OL baseline.

Simpson-Angus Scale (SAS)

The SAS is a clinician-rated assessment of neuroleptic-induced Parkinsonism consisting of 10 items (each ranging from 0 to 4). SAS mean score is calculated as the average of all 10 item scores. Lower values of SAS mean score indicate milder symptoms. If any item score is missing, the mean score will be set to missing.

SAS mean score (observed value and change from both the DB baseline and the OL baseline) will be summarized numerically by visit. In addition, SAS mean score at each visit will be classified as “abnormal” if it exceeds 0.3. Otherwise, non-missing mean scores will be classified as “normal”. Shifts from baseline in SAS mean score classification will be summarized by visit and overall for all post-OL baseline assessments during the open-label extension period, using both the DB baseline and the OL baseline.

Document: Documentation\SAP

Author:

Version Number:

Final V1.0

Version Date:

27FEB2019

Template No: CS_TP_BS016 Revision 4
Effective Date: 01Apr2016

Reference: CS_WI_BS005

Copyright © 2009, 2010, 2012, 2016 Quintiles Transnational Corp. All rights reserved.

The contents of this document are confidential and proprietary to Quintiles Transnational Corp. Unauthorized use, disclosure or reproduction is strictly prohibited.

All data from the three scales will be presented in the data listings.

17.5.2. PITTSBURGH SLEEP QUALITY INDEX (PSQI)

The Pittsburgh Sleep Quality Index (PSQI) contains 19 self-rated questions and 5 questions rated by the bed partner or roommate (if one is available). Only self-rated questions are included in the scoring. The 19 self-rated items are combined to form seven “component” scores, each of which has a range of 0-3 points. The seven component scores are then added to yield one global score, with a range of 0-21 points, “0” indicating no difficulty and “21” indicating severe difficulties in all areas (Buysse et al. 1989).

If any of the component scores are missing, the PSQI global score will be set to missing. The PSQI scoring algorithm as downloaded from the University of Pittsburgh Sleep and Chronobiology Center is inserted in Appendix 4.

Observed PSQI global score at both the DB baseline and the OL baseline, and at each scheduled post-OL baseline extension visit and LOCF, will be summarized for the safety population. Change from baseline in PSQI global score will also be summarized for each scheduled post-OL baseline extension visit and LOCF, based on both the DB baseline and the OL baseline.

17.5.3. DRUG EFFECTS QUESTIONNAIRE (DEQ)

The Drug Effects Questionnaire (DEQ) consists of 3 questions scored on a visual analog scale (VAS).

Data from the DEQ questionnaire at both the DB baseline and the OL baseline, and at each scheduled post-OL baseline extension visit and LOCF, will be summarized for the safety population. Change from baseline will also be summarized for each scheduled post-OL baseline extension visit and LOCF, based on both the DB baseline and the OL baseline. For Describe Drug Effect and Like Drug Effect, if the Result is “Negative”, the numeric measurement will first be converted to a negative number before being summarized.

17.5.4. COLUMBIA SUICIDE SEVERITY RATING SCALE (C-SSRS)

The C-SSRS is a tool designed to systematically assess and track suicidal behavior and suicidal ideation throughout the study. The strength of this suicide classification system is in its ability to comprehensively identify suicidal events while limiting the over-identification of suicidal behavior. The C-SSRS Baseline/Screening Version is used at the screening visit of study 361-201 and the C-SSRS Since Last Visit Version is used from Visit 2 onward in study 361-201 and at all visits in study 361-202. Subjects with Type 4 (active suicidal ideation with some intent to act, without specific plan) or Type 5 (active suicidal ideation with specific plan and intent) suicidal ideation during the study will be discontinued from the study and referred to a mental health professional.

C-SSRS includes four sections: Suicidal Ideation, Intensity of Ideation, Suicidal Behavior, and Answer for Actual Suicide Attempts.

The following outcomes are C-SSRS categories and have binary responses (yes/no). The categories are re-ordered from the scale to facilitate the definitions of the C-SSRS endpoints, and to provide clarity in the presentation of the results.

Document: Documentation\SAP

Author:

Version Number:

Final V1.0

Version Date:

27FEB2019

Template No: CS_TP_BS016 Revision 4
 Effective Date: 01Apr2016

Reference: CS_WI_BS005

Copyright © 2009, 2010, 2012, 2016 Quintiles Transnational Corp. All rights reserved.

The contents of this document are confidential and proprietary to Quintiles Transnational Corp. Unauthorized use, disclosure or reproduction is strictly prohibited.

Statistical Analysis Plan

Suicidal ideation is measured by 5 categories, representing 5 subtypes of suicidal ideation with increasing severity:

Category 1: Wish to be Dead

Category 2: Non-specific Active Suicidal Thoughts

Category 3: Active Suicidal Ideation with Any Methods (Not Plan) without Intent to Act

Category 4: Active Suicidal Ideation with Some Intent to Act, without Specific Plan

Category 5: Active Suicidal Ideation with Specific Plan and Intent

Suicidal behavior is measured by 5 categories, representing 5 subtypes of suicidal behavior:

Category 6: Preparatory Acts or Behavior

Category 7: Aborted Attempt

Category 8: Interrupted Attempt

Category 9: Actual Attempt (non-fatal)

Category 10: Completed Suicide

The 10 categories above are not mutually exclusive. Subjects will be counted in each category for which they have an event.

Self-injurious behavior without suicidal intent is a non-suicide-related C-SSRS outcome, and also has a binary response (yes/no).

For the purpose of C-SSRS analysis, “baseline” and “post-OL baseline” are defined as follows.

Time point	Study Visit	C-SSRS Version	Derivation Rule
DB Baseline	Screening/Visit 1 of study 361-201	Baseline/Screening – Past 1 Month	Most severe outcome
	Randomization/Visit 2 of study 361-201	Since Last Visit	
OL Baseline	Week 4/Visit 7 of study 361-201	Since Last Visit	As collected for that visit
Post OL Baseline Extension Period	All post OL baseline extension visits up to and including Week 26/Visit 11E, including unscheduled visits	Since Last Visit	Most severe outcome

C-SSRS composite endpoints will be derived for each time point of interest (i.e. DB baseline, OL baseline, post OL baseline extension period, and each extension study visit) as follows:

- Any suicidal ideation: A “yes” answer to any one of the 5 suicidal ideation questions on C-SSRS

Document: Documentation\SAP

Author:

Version Number:

Final V1.0

Version Date:

27FEB2019

Template No: CS_TP_BS016 Revision 4
 Effective Date: 01Apr2016

Reference: CS_WI_BS005

(Categories 1-5).

- Any suicidal behavior: A “yes” answer to any one of the 5 suicidal behavior questions on the C-SSRS (Categories 6-10).
- Any suicidality: A “yes” answer to any one of the 10 suicidal ideation and behavior questions on the C-SSRS (Categories 1-10).

For each subject, the suicidal ideation score at each time point of interest (i.e. DB baseline, OL baseline, post OL baseline extension period, each extension study visit, and the Week 26 LOCF endpoint) is defined as the maximum suicidal ideation category (1-5) present for the time of interest. If no ideation is present a score of 0 is assigned. A suicidal ideation score of 4 or 5 is considered serious.

The number and percentage of subjects with any suicidality, any suicidal ideation and subtypes of ideation, any suicidal behavior and subtypes of behavior, and any non-suicidal self-injurious behavior will be presented for:

- DB Baseline (as defined above)
- OL Baseline (as defined above)
- Post OL baseline extension period (as defined above)
- Each scheduled post OL baseline extension study visit, including Week 27/Visit 12E.

Shift in suicidal ideation score from baseline to the post OL baseline extension period and to each scheduled post OL baseline extension visit will be presented, using both the DB baseline and the OL baseline.

Intensity of ideation for the most severe ideation subtype is measured in terms of frequency, duration, controllability, deterrents, and reasons for ideation. Each is measured with responses ranging from 0 to 5 for frequency and duration, and from 1 to 5 for controllability, deterrents, and reasons for ideation. The ideation intensity total score is the sum of responses to the five items and can range from 2 to 25 for subjects with endorsed suicidal ideation. If one or more of these five items are missing at an assessment, the total score will be set to missing. If a subject did not endorse any suicidal ideation, a score of 0 for the ideation intensity total score will be given.

Actual lethality associated with actual attempts is rated on a 6-point scale from 0 = ‘No physical damage or very minor physical damage’ to 5 = ‘Death’. Potential lethality of actual attempts (if actual lethality = 0) is rated on a 3-point scale from 0 = ‘Behavior not likely to result in injury’ to 2 = ‘Behavior likely to result in death despite available medical care’.

The ideation intensity total score and the actual lethality and potential lethality of actual attempts will be presented in data listings.

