- ^d All study drug will be taken once daily in the evening by mouth.
- ^e Telephone calls will be made by a member of the research staff to the subjects between scheduled study visits (between Weeks 1 and 2, and at Weeks 5, 7, 9, 11, 13, 15, 17, 19, 21, 23, and 25) to monitor clinical symptoms and adverse events. If subject appears to be symptomatic, an unscheduled visit will be made as early as possible.
- ^f Procedures and assessments for unscheduled visit are: drug accountability, physical and neurological examination, vital signs, ECG, clinical laboratory tests, urine drug screen, PANSS, CGI-S, MADRS, BNSS, AIMS, BARS, SAS, and C-SSRS.
- ^g Vital signs will include supine and standing measurements of blood pressure and heart rate and respiratory rate and temperature.
- ^h Clinical laboratory tests include: hematology, serum chemistry, urinalysis, serum prolactin, glycosylated hemoglobin (HbA_{1c}), and glucose and lipid panel (subjects must be fasted [no food or drink except water at least 8 hours] prior to collection of blood samples for glucose and lipid panel).
- ⁱ Blood samples for determination of plasma SEP-363856 and SEP-363854 concentrations will be collected at Visit 2E, 5E, 8E, and 11E (time and date of the 3 previous doses of study medication and the time of the blood sampling must be recorded). Time of food intake relative to study drug taken should be recorded.
- ^j Urine drug screen may be ordered at other visits as deemed clinically appropriate. These results should be discussed with the Medical Monitor.
- ^k Any positive urine β -hCG test should be confirmed by a serum β -hCG test.
- ^l Unscheduled BARS, AIMS, and SAS scales should be administered if a subject develops extrapyramidal symptoms (EPS) requiring treatment. See [Section 10.3](#).
- ^m Titration up to 75 mg/day is permitted (but not required) on Day 4 for reasons of efficacy as an unscheduled visit. At the minimum Investigator will assess AEs, concomitant medications and perform drug accountability at Day 4 unscheduled visit, all other assessments are not required but permitted based on Investigators judgment.

Note: With the exception of the DEQ and the USPA-B, all rating assessments will be performed by the rater using a tablet. In the event that a tablet is not available, the rating assessments will be performed by the rater using a paper version of the assessment.

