11.6.11. Unscheduled Visit (Subjects Who Appear Symptomatic during Telephone Contacts)

If subject appears to be symptomatic during a telephone contact, an unscheduled visit will be made as early as possible. The following procedures will be conducted during this visit:

- Study drug accountability
- AE monitoring
- Prior/concomitant medications
- Physical and neurological examination
- Vital sign measurements (prior to ECG)
- Perform standard 12-lead ECG
- Physical and neurological examination
- Fasted blood samples for clinical laboratory evaluation (hematology, serum chemistry, serum prolactin, glycosylated hemoglobin [HbA_{1c}], glucose panel and lipid panel)
- Urine sample for urinalysis, UDS, and β hcG (for female subjects)
- PANSS
- BNSS
- MADRS
- C-SSRS
- CGI-S
- AIMS
- BARS
- SAS

If a subject titrates up to 75 mg/day on Day 4 (permitted but not required) an unscheduled visit must occur. The following procedures will be conducted during this visit:

- Study drug accountability
- AE monitoring
- Prior/concomitant medications

Other assessments are not required on Day 4, but are permitted, based on Investigators judgment.

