15.3.6.7. Suicidality Measure

Frequency and severity of suicidal ideation and suicidal behavior as measured by the C-SSRS scale will be summarized for each visit.

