6.4. RETESTS, UNSCHEDULED VISITS AND EARLY TERMINATION DATA

In general, for by-visit summaries, data recorded at the scheduled visits will be presented.

Unscheduled measurements will not be included in by-visit summaries. Unscheduled measurements collected prior to the first dose of study medication in study 361-201 will contribute to the derivation of the DB baseline value. Unscheduled measurements collected prior to the first dose of extension study medication in study 361-202 will contribute to the derivation of the OL baseline value. Unscheduled measurements collected post OL baseline will contribute to the derivation of the LOCF endpoint, potentially clinically significant (PCS) value, best/ worst case value where required (e.g. shift tables), and identification of a relapse event (see section 16.2.6).

Early termination data collected post OL baseline will be assigned to the next planned visit for that assessment. This mapping will be done for all data points used in the efficacy and safety analyses.

In the case of a retest (same visit number assigned), the latest available measurement for that visit will be used for by-visit summaries.

Listings will include scheduled, unscheduled, retest and early termination data.

Document: Documentation\SAP

Author:

Version Number:
Version Date:

Final V1.0
27FEB2019

Template No: CS_TP_BS016 Revision 4
Effective Date: 01Apr2016

Reference: CS_WI_BS005

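### The by-visit C-SSRS tables leave out unscheduled assessments although the form looks back only to the last visit, so some suicidality can be missing from every by-visit row

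*SAP*

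**What the plan says.** **Collection.** Protocol 11.6.11 states: "If subject appears to be symptomatic during a telephone contact, an unscheduled visit will be made as early as possible". The C-SSRS is among the procedures listed for that visit. The unscheduled-visit footnote to the schedule of assessments (Protocol Table 2) agrees; its list of scales reads "PANSS, CGI-S, MADRS, BNSS, AIMS, BARS, SAS, and C-SSRS". SAP 17.5.4 says that "the C-SSRS Since Last Visit Version is used from Visit 2 onward in study 361-201 and at all visits in study 361-202".

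**Planned summary.** Protocol 15.3.6.7: "Frequency and severity of suicidal ideation and suicidal behavior as measured by the C-SSRS scale will be summarized for each visit".

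**Analysis rules.** SAP 6.4: "Unscheduled measurements will not be included in by-visit summaries". SAP 17.5.4 then presents two kinds of display:

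- Counts. One set is for "Each scheduled post OL baseline extension study visit, including Week 27/Visit 12E". The others are for the two baselines (DB and OL) and for the whole extension period pooled.
- Shifts in the ideation score, from each baseline to the pooled period and to the scheduled visits one by one.

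The pooled period is the most severe outcome over "All post OL baseline extension visits up to and including Week 26/Visit 11E, including unscheduled visits". SAP 17.5.4 gives no comparable derivation for a single extension visit, and it has no rule that carries an unscheduled C-SSRS result into a scheduled-visit row.

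**The concern.** Leaving unscheduled values out of by-visit tables costs little for a measure of current state such as PANSS or blood pressure, because the same state is rated again at the next scheduled visit. The Since Last Visit C-SSRS records what happened over an interval. Once a form has been completed at an unscheduled visit, the next scheduled form, read plainly, asks only about the time after it. An attempt, a self-injury, or an ideation episode that is over by the unscheduled visit then belongs to the unscheduled record, which the by-visit tables omit.

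The omission is not random. These assessments are made because the subject seemed symptomatic on a call, so any error in the by-visit percentages and by-visit ideation shifts is toward too little suicidality. C-SSRS frequency and severity is a secondary endpoint, and Protocol 15.3.6.7 specifies that it be summarized by visit.

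**Working it through.** The plan states no figure to reproduce here. The check applies the two SAP rules to one invented subject and then looks at what is known about size.

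**Inputs**

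- Scheduled post-baseline C-SSRS visits (Protocol Table 2): Days 8, 15, 22, 29, 57, 85, 113, 141, 169, 183 and 190, which is 11 visits.
- Planned telephone calls (Protocol 7.1): one between Weeks 1 and 2, plus Weeks 5, 7, 9, ..., 25, so 1 + 11 = 12.
- Anticipated enrolment (Protocol 15.1): about 180.
- Invented for illustration: Category 3 ideation on Day 62 that resolves and does not recur; an unscheduled C-SSRS on Day 64, about the time of the Week 9 call.

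**Trace through SAP 6.4 and 17.5.4**

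| Case | Week 12 form covers | Positive by-visit rows | Pooled maximum to Week 26 | Week 26 LOCF score |
|---|---|---|---|---|
| (a) No unscheduled visit | Days 57 to 85 | 1 | 3 | 0 |
| (b) Unscheduled C-SSRS on Day 64, window restarts | Days 64 to 85 | 0 | 3 | 0 |
| (c) Unscheduled C-SSRS on Day 64, rater looks back to last scheduled visit | Days 57 to 85 | 1 | 3 | 0 |

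Between (a) and (b) only the extra assessment differs, and it removes the event from the by-visit table and the by-visit shift. The pooled row is the same in all three cases. The LOCF score does not recover the event, because later negative forms supersede it.

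**With the proposed rule**, the Week 12 outcome is the maximum over the Day 64 and Day 85 forms. In (b) this is max(3, 0) = 3 and in (c) max(3, 3) = 3. The by-visit count is 1 in both, so the rule gives the right answer whichever meaning of last visit the raters used.

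**How much of an interval is exposed.** If the unscheduled visit falls at week u between scheduled weeks a and b, the share of calendar time outside the next scheduled form is (u − a)/(b − a):

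- Calls at Weeks 5, 9, 13, 17, 21: for example (5 − 4)/(8 − 4) = 25%.
- Calls at Weeks 7, 11, 15, 19, 23: for example (7 − 4)/(8 − 4) = 75%.
- Call at Week 25: (25 − 24)/(26 − 24) = 50%.

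These figures assume that the visit takes place at about the time of the call. They describe calendar time for one subject who has such a visit, not a share of events lost.

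**Effect on a row.** One omitted subject changes a by-visit percentage by 1/180 = 0.56 points if all 180 are assessed at that visit, and by more if fewer remain. As a purely assumed example, let 4 of 180 subjects have a finding in an interval. With 0, 2 or 4 of them reported only at an unscheduled visit, the row shows 4/180 = 2.2%, 2/180 = 1.1% or 0/180 = 0%. The documents do not say which is realistic.

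**The case against.** The strongest reply is that the safety question is already answered elsewhere. The pooled row in SAP 17.5.4 includes unscheduled visits and takes the most severe outcome for every ideation and behavior category and for self-injury, and an ideation shift to that period is also planned. Unscheduled results are listed, and they feed the relapse search where the SAP Appendix 3 criteria apply. The study tests no hypothesis. All of this stands, and it confines the point to the by-visit displays.

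Other parts of the reply:

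- *The restart is an inference.* This stands. Neither document says whether the last visit means any visit or the last scheduled one, and a rater using the second meaning closes the gap (case c). The restart is still the plain reading, because the SAP's own table applies the Since Last Visit form to unscheduled visits.
- *Early-termination data are mapped to the next planned visit* (SAP 6.4), and Type 4 or 5 ideation leads to discontinuation. This stands in part. A finding on a record made as an early-termination visit does appear by visit. Lower-grade ideation, or behavior or self-injury in a subject who continues, has no such route. Ideation that persists or recurs after the unscheduled visit also reaches the next scheduled row.
- *SAP 6.4 lets unscheduled values supply worst-case values in shift tables.* This does not settle it, because SAP 17.5.4 separately specifies a shift to each scheduled visit.
- *By-visit and pooled rows differ for a stated reason.* This stands. A reader might infer an unexplained conflict between the tables, but SAP 6.4 and 17.5.4 together explain the difference.
- *The endpoint has no by-visit element.* This stands for Protocol 6.2, which names only frequency and severity. The by-visit form comes from the analysis section, 15.3.6.7.

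**Conclusion.** The point holds for the by-visit counts and by-visit ideation-score shifts only. On the plain reading of the form, suicidality that is reported at a symptom-triggered unscheduled visit and does not recur can be absent from every by-visit row, so the summary in Protocol 15.3.6.7 is biased downward. The conclusion rests on the recall window restarting at an unscheduled C-SSRS and on the visit not being recorded as early termination.

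The size is unknown, because the documents do not say how often unscheduled visits occur or how often they yield a positive C-SSRS.

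Three stronger readings are tempting, and the documents do not support them:

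- That suicidality drops out of the analysis. The pooled count and shift to Week 26 and the listings retain it.
- That the timing of suicidality cannot be seen at all. Findings from scheduled and early-termination visits are still shown by visit, and unscheduled findings are listed.
- That up to 75% of events are lost. That figure is calendar time in one interval for a subject who has an unscheduled visit.

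This is a modest defect, worth correcting because the correction is cheap and extends the most-severe-outcome rule that the SAP already uses for DB baseline and the pooled period.

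**What to change.** In SAP 17.5.4, as a stated exception to 6.4:

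1. Define the C-SSRS outcome for each scheduled extension visit as the most severe answer across that visit and any unscheduled C-SSRS since the previous scheduled visit.
2. If no later scheduled or early-termination visit occurs, assign the unscheduled result to the next planned visit, as 6.4 already does for early-termination data.
3. Apply this to the by-visit counts and the by-visit ideation-score shifts.
4. Footnote the tables to say that each row covers the interval ending at that visit.

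The cost is a short derivation text and a small programming change, with no new data and no change in conduct. The downside is that a finding is shown at the next scheduled visit rather than on its own date (Day 85 rather than Day 64 in the example), and by-visit percentages may be slightly higher. The listings still give the actual date.
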